Rationale for PPJ. *Why combine daily life review (including gratitude interventions) with planning for the future (activity scheduling) in a daily exercise?* Gratitude interventions and activity scheduling should reinforce and extend each other’s impact. A positive correlation between higher levels of gratitude and greater behavioral activity have been reported.^{29,30} This association may be causal: in previous research, gratitude has been shown to improve affect^{17,31} which has been shown to encourage more frequent and more diverse types of activity.³² Therefore, gratitude intervention should encourage positive, abstinent behavior. Conversely, activity scheduling will enhance gratitude by guiding individuals to shape

their own positive experiences rather than to passively notice them.

Positive behaviors will produce content to populate the next day's gratitude inventory.

3. The next phase of this study will add to the existing knowledge base because we will collect more information about PPJ's feasibility, acceptability and impact with a larger sample size. Our development study included only women; this phase of the study will include women and men. We will also have a control group in this next phase of the study. We will also modify the protocol so we can conduct the study on Zoom to comply with shelter-in-place orders and COVID19 best practices Study Endpoints/Events/Outcomes

- 3.1. Primary Endpoint/Event/Outcome: The primary outcome is empirical data on the feasibility and acceptability of PPJ. We will also assess rates of substance use and treatment retention as primary outcomes.
- 3.2. Secondary Endpoint(s)/Event(s)/Outcome(s): These include hypothesized mediators of the effect of the intervention on outcomes. These include: mood, satisfaction with life, commitment to sobriety, alcohol and drug craving, anxiety, and depression. For a complete list, see the measures section 5.2.

4. Study Intervention(s)/Interaction(s)

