 - What kind of journals or diaries do you keep, if any? (If in the treatment group, what kinds in addition to PPJ?) Tell me about your use of journals or diaries over the past month.

PROTOCOL TITLE: Journaling and Addiction Recovery

VERSION DATE: 13 April 2021

- Tell us about any gratitude practices you have been doing over the past month, if any. (For treatment group, ask about any gratitude practices in addition to PPJ).
- Tell us what the 10th step means to you. What kind of 10th step have you been doing, if any, over the past month? (For the treatment group, ask if they have been doing any 10th step in addition to PPJ).
- What kind of planner or calendar do you keep, if any? What has your use of this planner been like over the past month? (for the treatment group, what have they been doing in addition to PPJ, if anything?)
- (at exit interview and follow up interview) Tell us about any times that you talked about your experience being in this study with other people, such as family members, housemates, your counselors, or others, if at all.

Effort, Feasibility, and Acceptability.

- # of Qualtrics surveys completed
- Effort, Ease, helpfulness, satisfaction (one item to assess each: “For this PPJ, I would say I put forth this much effort...” Degree to which PPJ was difficult, helpful, satisfying, easy, rated on a 0-10 point scale)
- # of group sessions attended
- # homework assignments completed
- # journal entries completed
- Eligibility rate: Number eligible/total at NUWAY site
- Consent rate: Number consented/number screened
- Group completion rates
- Independent practice phase completion rates
- # PPJs uploaded
- # PPJs completed
- % of PPJs completed out of total # of possibilities to complete PPJ
- # of items entered under each category
- Qualitative data from group discussion and exit interviews

Open-ended survey question.

- What thoughts would you like to share with us about being in this research study, if any?

Outcomes.

PROTOCOL TITLE: Journaling and Addiction Recovery

VERSION DATE: 13 April 2021

- Recurrence of substance use.
- Retention of treatment in NUWAY
- NUWAY reason for leaving
- Qualitative data from group discussion or exit interviews

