5. Participants may also be placed on the waiting list if: a) they will not be at NUWAY for the duration of the study, b) research staff is not sure if the person is eligible based on results of screening tests. In this case, NUWAY counseling staff are consulted to make sure the participant is eligible (e.g., if the person is adequately stabilized psychiatrically for participation).
6. Participant will be asked to write a list of 5 things that happened yesterday, research staff will evaluate this list and determine whether or not it is adequate for study inclusion. If not adequate, screening procedure will stop.
7. Research staff will administer the GAIN Cognitive Impairment Screener.⁵⁷ This instrument uses 6 items to determine cognitive impairment. It uses questions such as “What year is it now?” and “Please count backwards from 20 to 1.” Participants earn points for correct answers. Cognitive impairment is considered to be present if the total score is greater than 10. If the participant scores 14 or greater, they will be excluded from the study. Screening procedure will stop.

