12.1. Recruitment process. Recruitment will take place one of four ways. 1) NUWAY staff will reach out to clients who appear to meet study criteria. Clients might receive the electronic or hard copy recruitment flyer from their counselor. Clients then will be encouraged to contact study staff. 2) NUWAY staff will complete a release of information form with their clients allowing communication between NUWAY and the research team. NUWAY staff will inform research staff of client contact information, and study staff will reach out to clients (only if the release of information has been signed, unless the counselor is facilitating an introduction based on the in-group recruitment presentation, see #3, for example, a counselor might provide contact information for a client attending the recruitment presentation who needed assistance emailing or texting us directly). 3) Study staff will make presentations in NUWAY treatment groups (currently only to take place via Zoom), making the basic points from the recruitment flyer (see recruitment PowerPoint, attached). Clients then will be encouraged to contact study staff. 4) The recruitment flyer might be posted on bulletin boards or made available in group rooms or lounge areas on site (now that more clients are coming into the site in person) and clients can reach out to study staff based on information from the flyer. 5) When clients are scheduled for a screening by research staff, we will let the counselor know to begin the Release of Information procedure and we will let the counselor know of the date and time of the screening appointment. The purpose of this is to have the counselor help the client to follow through with attending the screening appointment (currently our rate of cancellations and no-shows for screenings is 51%) . Counselors, when helping with recruitment, will be advised by us that they must emphasize that participation is entirely optional and that clients may choose to participate or not, and may drop out, cancel the screening appointment, reschedule the screening appointment, or continue with the study as they wish. Prospective participants' relationships with NUWAY or the University of Minnesota will not be negatively compromised whatever choice they make, and this point will be emphasized.

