21.1. Compensation for Research-Related Injury: N/A

21.2. Contract Language: N/A

22. Consent Process

22.1. Consent Process (when consent will be obtained): Our consent process is informed by the instructions provided in HRP-090 and HRP-091. The consent process will take place on site at NUWAY (for electronic administration, it will take place via Zoom). Research staff will meet with prospective participants. First, participants will complete a screening informed consent document then they will be screened using our screening document (attached to ETHOS). If the participant meets eligibility, we will offer the participant the choice of reading the informed consent document and we will verbally summarize it for them in detail. Participants will be administered the UBACC quiz to determine that they have understood the study and their role in the study. A score of 15 or higher is needed for inclusion in the study. An impartial witness will be used if necessary, for example, if the prospective participant has a visual impairment and cannot read the informed consent document. If an impartial witness is used we will follow the guidelines described in HRP-090 for that procedure.

22.2. Waiver or Alteration of Consent Process (when consent will not be obtained, required information will not be disclosed, or the research involves deception): N/A

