As of August 2020, we will also be recruiting from a second NUWAY site, "NUWAY III." NUWAY III is located at [name]. NUWAY III is a medium-intensity residential treatment program for women and transgender people. The program provides comprehensive treatment for substance use and mental health disorders and has the capacity for 31 women and transgender people. NUWAY III offers gender-informed curriculum, treats trauma, and offers individual and group therapy.

As of September 2020, we will also be recruiting from a third NUWAY site, "2118." Nuway's [name] location in Minneapolis, MN, serves over 220 outpatients each year. Nuway is an extended care outpatient facility where clients attend treatment 4 hours per day, Monday through Friday, for 90-120 days. "2118" is a 20,000 square foot facility featuring 10 group rooms, 16 offices assigned to counseling staff, five therapy offices, several client lounges including five designated as quiet

areas, a cafeteria for clients, a lecture hall that seats 135 people, a smoking area, and an outdoor green space. “2118” has 15 full-time licensed clinicians, two clinical supervisors, one program director, one executive program director, three admissions staff, three information technology support staff, 6-10 interns from various counseling programs throughout the Twin Cities, and 2-4 floating therapists who fill in as needed.

All study procedures are the same for all NUWAY sites.

2. International Research: N/A
3. Community Based Participatory Research: N/A

2. Multi-Site Research

N/A

3. Resources Available

3.2. Resources Available:

Time. The Agricultural Experiment Station (AES) grant that is funding this study provides PI [name] with one course buy out for the academic year 2019-2020. PI [name] will use this time and additional time to conducting and completing this research.

Research Assistant(s) (RA). The AES grant that is funding this study allows for two 25% RAs for the 2019-2020 school year and two 25% RAs for the 2020-2022 school year. One RA will be dedicated to this study. The CTSI grant will also provide a second RA. The RAs will be involved in all aspects of the research including screening and informed consent, data management, data cleaning, literature reviews, exit interviews, attending group sessions, and general research activities.

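### The consent rate mixes ineligibility with unwillingness, and the eligibility rate rests on a denominator with no fixed time window

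*Combined protocol and SAP*

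**What the plan says.** Section 3.1 states: "The primary outcome is empirical data on the feasibility and acceptability of PPJ". It then names substance use and treatment retention as primary outcomes as well. Under Effort, Feasibility, and Acceptability, the Measures part of Section 5.2 defines "Consent rate: Number consented/number screened" and "Eligibility rate: Number eligible/total at NUWAY site". Table 2 schedules both rates for both arms among the final study activities.

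Section 22.1 fixes the order of steps: "First, participants will complete a screening informed consent document then they will be screened using our screening document". Only then: "If the participant meets eligibility, we will offer the participant the choice of reading the informed consent document". Section 9.3 shows screening ending before main consent. After the short writing task, for example: "If not adequate, screening procedure will stop". The same section lets people eligible for the wait list sign the main consent, and they can include people whose eligibility is still uncertain.

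On attendance, Section 12.1 reports, as a percentage, "currently our rate of cancellations and no-shows for screenings is 51". On site size, Section 23.1 gives 288 clients currently served at the first site, a capacity of 31 at the second, and a third that "serves over 220 outpatients each year". Section 8.1 describes rolling enrolment in a study lasting about two years.

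**The concern.** A consent rate is normally read as willingness among people who could have said yes. Here the denominator also holds people who were never offered main consent. A low figure could mean strict criteria or reluctant clients, and a later trial would answer those two problems differently.

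An eligibility rate is normally read as the share of assessed people who meet the criteria. Here the denominator is everyone at a site, although the recorded assessments do not clearly cover everyone. The site totals are also given as a current census, a bed capacity and an annual flow, so the same count of eligible people can produce very different percentages.

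Both rates sit under a primary outcome. One stated study step in Section 5.2 is to study and refine recruitment, which needs to know where people are lost.

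**Working it through.** The plan gives no expected value, precision or threshold for either rate, so there is no figure to reproduce. The check is algebra on the definitions.

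**Inputs from the documents**
- The two formulas (Section 5.2, Measures).
- Screening before main consent (Sections 9.3 and 22.1).
- 51% of booked screenings cancelled or missed (Section 12.1).
- 288 current clients and stays generally of 90 to 120 days at the first site (Section 23.1).
- About 100 people to be consented (Section 11.1).
- About two years of study (Section 8.1).

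**Assumptions, not in the documents**
- e = share of screened people who are eligible, 0.5 to 1.0.
- c = share of eligible people who consent, 0.7 to 0.9.
- a = share of the site that is assessed, 0.1 to 1.0.
- Only eligible people sign main consent. Wait-listed signers break this and are taken up under the objection.

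**Consent rate.** Consented/screened = (eligible/screened) × (consented/eligible) = e × c.

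| e | c = 0.90 | c = 0.70 |
|---|---|---|
| 1.0 | 0.90 | 0.70 |
| 0.9 | 0.81 | 0.63 |
| 0.7 | 0.63 | 0.49 |
| 0.5 | 0.45 | 0.35 |

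The value 0.63 appears twice, once with 90% willingness and 70% eligibility and once the other way round. The ratio cannot tell these apart. For 100 consents at c = 0.90 there are 100/0.90 = 111 eligible people. The number screened is 111.1/e, so the ineligible people in the denominator number about 12 at e = 0.9 (123.5 − 111.1), 48 at e = 0.7 (158.7 − 111.1) and 111 at e = 0.5 (222.2 − 111.1).

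**Eligibility rate.** If eligibility is counted at the research screening, eligible/site total = a × e. With e = 0.80, the result is 0.08, 0.20, 0.40 or 0.80 when 10%, 25%, 50% or 100% of the site is assessed. It equals e only when everyone is assessed.

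**Time window.** Take 288 places, always full, over 730 days. At 120-day stays, 288 × 730/120 = 1,752 clients pass through. At 90-day stays, 288 × 730/90 = 2,336. Against a census of 288, the denominator differs by a factor of 6.1 to 8.1 for the same numerator.

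**Attendance.** If 49% of bookings take place, 100 interviews correspond to 100/0.49 = 204 bookings. These are appointments, not necessarily 204 people. If *screened* means interviewed, people who never attend are not in the consent denominator at all.

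**The case against.** **The consent ratio is useful as a yield.** This stands. At 72%, for example, 100 consents need 100/0.72 = 139 screenings, and that is correct. A reader might infer that the formula would misplan a larger trial's recruitment. The documents do not support this: Section 17.3 feeds descriptive statistics into later sample-size work but does not mention these rates, and a yield ratio plans interviews properly.

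**Ineligible people are not labelled refusals.** This stands. A reader might say that the plan counts them as refusals, but the plan never calls the ratio a refusal or willingness rate. The defect is that the ratio cannot be read as one.

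**Pre-screening may make nearly everyone at interview eligible.** This is possible. Staff and telephone pre-screens come first, and as e approaches 1 the gap closes. The plan does not say which of these stages defines *screened*.

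**The eligibility denominator may be the right one.** This stands in part. Section 5.1 has counselors review their caseloads against a check sheet, and a complete, tallied review would support a site-wide rate. But no tally is specified, checklists are completed for referred clients, and the procedural steps in Section 5.2 end staff action once a client is not interested. It is therefore too strong to say outright that unassessed clients are counted as ineligible.

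**The 51% does not show where most people are lost.** This stands. Missed appointments can be rescheduled, earlier declines are not reported, and Section 12.1 cites the figure as the reason for a new step to raise attendance.

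**The direction of bias is not settled.** This stands. Screen failures pull the consent rate down, while wait-listed signers and absent non-attenders push it up.

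**A cleaner denominator is not trivial.** This stands too. The UBACC, the capacity quiz, follows the consent discussion, so someone who declines during that discussion has no final eligibility status.

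**Conclusion.** The concern holds for the consent rate and in a smaller form for the eligibility rate.

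The consent rate follows a stated rule that combines two quantities. With 90% willingness it would read 81%, 63% or 45% as the eligible share falls from 90% to 70% to 50%. These shares are assumed; the algebra is not. The eligibility rate lacks a time window and a stated source for its numerator. The six- to eight-fold range in its denominator assumes constant full occupancy at one site.

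The consequence is limited. The analysis paragraph on primary feasibility measures in Section 5.2 gives examples that do not include these two rates, and no test, progression threshold or sample size uses them. The underlying counts should be recoverable later. What is affected is how feasibility is interpreted and how recruitment is planned. Priority is low to moderate.

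**What to change.** Amend the definitions in Section 5.2 and report one participant flow, by site, with a 95% confidence interval for each rate. Count persons, not appointments, at each step: booked, interviewed, eligible at the research screening, signing main consent, randomised.

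- **Attendance rate:** persons interviewed / persons booked.
- **Eligibility rate:** persons eligible / persons assessed at the screening interview.
- **Consent rate:** persons signing main consent / persons meeting the criteria assessed before the consent discussion. Show UBACC failures and wait-listed signers separately.
- **Yield:** keep consented/screened under that label only, and state which screening stage it refers to.

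If a site-wide eligibility figure is still wanted, state the time window for each site's total and have the counselors' caseload review tallied in full.

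The cost is wording and tabulation. Section 5.1 already plans to hold screening, recruitment, enrolment and retention data in REDCap. The one thing to confirm is that bookings are recorded there by person. Design, visits and participant burden do not change.

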Open ended questions: Experience with 10 th step, journaling, gratitude practices, and using a planner.	4 minutes	Verbally administered using REDCap			Verbally administered using REDCap	Verbally administered using REDCap
What have you already heard about the study?	1 minute	Verbally administered using REDCap				
Hypothesized Mediators						
Positive and Negative Affect Schedule, including three items comprising the serenity subscale	2 minutes	X	X	X	X	X
Abstinence Self Efficacy Question (single item)	1 minute	X	X	X	X	X
Commitment to Sobriety (single item)	2 minutes		X	X	X	X
Alcohol craving (single item)	½ minute	X	X	X	X	X
Drug craving (single item)	½ minute	X	X	X	X	X
Happiness with Recovery (single item)	½ minute	X	X	X	X	X

PROTOCOL TITLE: Journaling and Addiction Recovery

VERSION DATE: 13 April 2021

Individual items to assess specific impact of PPJ journaling practice ¹ (attached as "single items to assess change")	3 minutes	X	X	X	X	X
Satisfaction with Life	1 minute	X	X	X	X	X
Quality of life scale, modified to compare quality of life during recovery ("now") to quality of life during active addiction ("then") ¹	3 minutes	X	Global quality of life item only	X	X	X
Flourishing scale	2 minutes	X		X	X	X
Treatment Group Only						
# of Qualtrics surveys completed				X	X	X
Ease, helpfulness, satisfaction, effort of PPJ (for control group, ease, helpfulness, satisfaction, effort of filling out the survey questionnaires)	2 minutes		X	X	X	
# group sessions attended				X		
# homework assignments completed				X		
# journal entries completed				X	X	
Count of # of items entered into PPJ		X	X	X	X	
Eligibility rate and consent rate (treatment and control group)						X
On approximately the fourth session of group (halfway through the total # of sessions) ask: "what is working for me in this journaling group is...." And "what is not working for me in this journaling group is...."						
Open Ended Survey Question						
Treatment group: What are your thoughts about Positive Peer Journaling (PPJ) so far?	2 minutes			X	X	
Outcomes						
Recurrence of Substance Use				X	X	X
Treatment Retention at NUWAY (successfully exiting treatment with staff approval versus against staff advice or at staff request)				X	X	X
Qualitative Exit Interview	45 minutes					X
1 month follow up interview	25 minutes					X

Baseline characteristics.

- Sociodemographics

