Secondary measures: outcomes and mediators. We will compare rates of treatment retention and recurrence of substance use to the general rates reported by NUWAY. We will also examine pre-post treatment means and standard deviations of hypothesized mediators (affect, satisfaction with recovery, individual items theoretically related to PPJ) to determine if change is in the expected direction. We will also study these constructs to determine if there is reasonable variability in the data we collect or if floor or ceiling effects are present. We may also use single-subject designs⁵⁶ to depict change over time in key constructs by study participant. Qualitative data will be thematically analyzed using the techniques recommended by Braun and Clarke.¹³ Here, the researcher examines transcripts of texts and identifies key themes and how themes relate to one another. These data will inform intervention development and study implementation procedures.

Data analytic techniques to compare treatment and control groups. While this pilot study will not be adequately powered to detect significant effects between treatment and control groups, we will compare differences between the treatment and control groups at baseline and over time using either t-tests or multi-level modeling. T-tests will reveal significant differences between groups and multi-level modeling will show whether rate of change is significantly different between groups.

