7.1. Participants will be encouraged to email or call the PI in about a year's time to obtain study results in the form of academic posters or academic manuscripts or other products. Upon such requests, the PI will email or send via regular mail these products as well as an easy-to-understand fact sheet summarizing the results to date, to improve accessibility to study findings for lay readers. This opportunity is mentioned in the informed consent document. In general, the PI will share research findings at community-based, local, regional, and international conferences, during class or other lectures, and will publish study findings in academic journals. We will also make a presentation of findings to NUWAY staff when the study is over and throughout the study, as requested by NUWAY.

8. Study Duration

8.1.

- The duration for an individual participant's participation in the study is anticipated to be five to nine weeks as follows: Phase 1: 2.5 weeks, Phase 2: 2 weeks, a qualitative exit interview to take place as soon as possible at the 5 week mark, and a follow-up interview approximately 30 days after the exit interview.
- The duration anticipated to enroll all study participants: Enrollment will be rolling. We will recruit 10-20 individuals at a time to populate 1-2 treatment groups and corresponding individuals for the control groups. This study will last approximately 2 years. Typically, we will screen and consent and enroll participants during the week before groups start.
- The duration anticipated to complete all study procedures and data analysis: Including manuscript production and publication, approximately four years.

9. Study Population

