9.1. Inclusion Criteria: 1) minimum 18 years of age, 2) meet DSM-V criteria for past-year SUD as primary or secondary diagnosis, 3) English literacy sufficient to make short written lists needed to complete PPJ and homework assessments, 4) minimum approximately 2 weeks sustained abstinence (ideally > 10 days), 5) completed first 2 weeks of treatment at NUWAY (approximately 2 weeks), 6) agree to be audio recorded / transcription recorded in group meetings and in individual meetings with research staff, 8) currently are clients at NUWAY, 9) participants must be English speaking and literacy must be strong enough to write short lists and to understand the questions asked in the Qualtrics survey, 10) have an email address and are willing to check it regularly and use it to receive study communications, 11) have a device that has a camera for Zoom

PROTOCOL TITLE: Journaling and Addiction Recovery

VERSION DATE: 13 April 2021

participation and to take pictures and is connected to the internet, such as a smartphone or tablet, 12) has access to high speed internet. Many NUWAY participants live in Sober Living Housing with internet provided. Priority will go to participants who will be in treatment at NUWAY for the duration of the study activities (and not discharging after one week, for example).

The participants in treatment at NUWAY are individuals with low or no income and histories of severe substance use disorder. Therefore in the list below we checked that they are “disadvantaged in the distribution of social goods and services such as income, housing, or healthcare” and, as individuals with addictive disorders, we also checked that they are from an “undervalued or disenfranchised social group.”

All participants will be 18 or over. NUWAY on occasion will have a client younger than 18, but they will not be eligible for this study.

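### The only analysis sentence that names retention and recurrence compares them with NUWAY's general rates; the randomised comparison, its test and its period are not named for them, and the power statements conflict on retention

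*Combined protocol and SAP*

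**What the plan says.** Outcome status. Section 3.1 puts feasibility and acceptability first and then adds: "We will also assess rates of substance use and treatment retention as primary outcomes". In the Analysis Plan (5.2) the same two outcomes fall under the paragraph on secondary measures.

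Named comparator. That paragraph says: "We will compare rates of treatment retention and recurrence of substance use to the general rates reported by NUWAY".

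Between-arm analysis. The paragraph of 5.2 on comparing the groups says: "we will compare differences between the treatment and control groups at baseline and over time using either t-tests or multi-level modeling". It names no outcome. Section 17.3 repeats the plan as t-tests for means and multi-level models for slopes, again naming no outcome.

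Definition and timing. Table 2 defines the outcome as "Treatment Retention at NUWAY (successfully exiting treatment with staff approval versus against staff advice or at staff request" and marks it at three points: after the group phase, after the independent practice phase, and at final activities including the one-month follow-up. Under 8.1, "participation in the study is anticipated to be five to nine weeks as follows". Section 23.1 gives outpatient stays of generally 90-120 days.

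Entry. Section 9.1 requires that participants have "completed first 2 weeks of treatment at NUWAY (approximately 2 weeks" and about two weeks of abstinence. It adds: "Priority will go to participants who will be in treatment at NUWAY for the duration of the study activities". Section 9.3 lets the abstinence requirement be waived on clinical judgement, and the pre-screen in 12.1 sets a 6-day minimum for both.

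Power. Section 17.2 uses N=76 from the original proposal and concludes that the current study should be adequately powered for retention with a two-tailed test. Section 17.3, directly after it, says the study is not adequately powered. Section 5.2 says: "While this pilot study will not be adequately powered to detect significant effects between treatment and control groups". Neither excepts retention. Section 11.1 now plans about 100 consented.

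**The concern.** The trial randomises, and the control arm passes through the same entry filters as the treatment arm. NUWAY's general rates need not. People who enter have already stayed for a time, have usually been abstinent recently, have passed psychiatric, cognitive and behavioural screening, and are preferred if expected to stay. A better rate than NUWAY's could follow from that selection alone.

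The between-arm comparison does not have this problem, but for these two outcomes its test and period are left open and could be settled after the data are seen. The period matters because retention is defined by manner of exit yet tallied at three points, and the plan does not say how someone still in treatment at the chosen point enters the comparison.

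The power conflict has its own consequence. A null retention result could be reported as coming from a powered comparison under 17.2, or as uninformative under 17.3 and 5.2.

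**Working it through.** **1. Where the two outcomes appear in the analysis text**

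| Place | Names retention or recurrence? | Comparator | Test |
|---|---|---|---|
| 5.2, secondary measures | Yes | NUWAY general rates | None |
| 5.2, comparing the groups | No | Other arm | t-test or multi-level model |
| 17.3 | No | Other arm | t-test and multi-level model |
| 17.2 | Yes, as yes/no outcomes | Other arm (implied) | Not named |
| 13.2 | Relapse and departure data kept for leavers | None | None |

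Section 17.2 is a power calculation and 13.2 a rule on keeping data. Neither states an analysis.

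**2. The plan's power figures**

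Inputs from 17.2: retention 96.6% v 75.9%; abstinence 41.5% v 24.8%; N=76. The allocation ratio is not stated; 1:1 is assumed, giving n=38 per arm.

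Arcsine formula: h = 2·asin(√p1) − 2·asin(√p2); power = Φ(h·√(n/2) − z).

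- Retention: h = 2.771 − 2.115 = 0.655; h·√19 = 2.857. One-sided 10% (z=1.282): Φ(1.575) = .942. Two-sided 5% (z=1.960): Φ(0.897) = .815.
- Abstinence: h = 1.400 − 1.043 = 0.357; h·√19 = 1.558. One-sided 10%: Φ(0.276) = .609. Two-sided 5%: Φ(−0.402) = .344.

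These match the stated .94, .82, .61 and .34. The conflict is between statements; the arithmetic is right.

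**3. Dependence on the test and on N**

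Two-sided 5%, same rates, no dropout; chi-square, t-test and Fisher by exact enumeration:

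| Outcome | n per arm | Arcsine | Uncorrected chi-square | t-test | Fisher |
|---|---|---|---|---|---|
| Retention | 38 | .815 | .821 | .821 | .682 |
| Retention | 50 | .906 | .908 | .900 | .822 |
| Abstinence | 38 | .344 | .343 | .343 | .264 |
| Abstinence | 50 | .431 | .426 | .426 | .349 |

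Fifty per arm is an upper case: 11.1 counts people consented, and 9.3 lets wait-listed people sign the main consent too.

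**4. Dependence on the assumed rates**

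The 17.2 rates come from behavioural activation studies. With control retention held at 75.9% and 38 per arm, chi-square power is .38 if treatment-arm retention is 90% and .17 if it is 85% (both rates illustrative).

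**5. Precision of the between-arm estimate**

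95% half-width = 1.96·√(p1q1/n + p2q2/n), with the 17.2 rates:

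- Retention: .148 at 38 per arm, .129 at 50.
- Abstinence: .208 at 38 per arm, .182 at 50.

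These assume independent participants. The journaling is taught in groups, which could widen them.

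**6. Size of the selection gap**

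This cannot be calculated. The documents give neither NUWAY's rates, nor the timing of drop-out, nor a maximum time in treatment at entry.

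**The case against.** The strongest reply is that this is a pilot whose main objective is feasibility, that the plan makes no efficacy claim from the NUWAY comparison, and that the between-arm paragraph excludes no outcome. Section 17.2 goes further: it computes two-group power for exactly these yes/no outcomes. All of that stands. A reader might infer that no randomised comparison of retention and recurrence is planned, or that the plan has no usable method for them. The documents do not support either reading: the comparison is implied, and a t-test can be applied to 0/1 data, with power close to that of the chi-square here. What is missing is a sentence assigning these outcomes to the comparison with a test and a period.

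A reader might also try to size the bias from the entry rules, or to show that follow-up always ends before a 90-120 day stay does. Neither can be established. The entry rules give minimum times in treatment and no maximum, so any such figure describes only the earliest entrants.

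Finally, one could say that the N=76 basis is disclosed and that a larger N only raises power. That is fair: it is an outdated basis, not an error. It does not remove the contradiction about retention.

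**Conclusion.** The point holds as a should-fix. Two outcomes that 3.1 calls primary are tied by name only to an external comparator that need not share the trial's entry filters, while the randomised comparison of them is left to inference, without test or period. The direction of concern is that a favourable gap could appear with no treatment effect; its size is unknown.

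The power statements contradict each other on retention. The .82 is arithmetically sound for 38 per arm, but it is conditional on 96.6% v 75.9% from another intervention and on the test (.68 with Fisher). It should not be inferred that 17.2 is the correct side and that 17.3 and 5.2 are simply wrong. The protocol's own development study (2.2) reports 73.3% discharged on good terms, below the assumed control rate, although in 15 women, with no control group, before the move to NUWAY. Abstinence is not powered on any calculation here: about .34 at 38 per arm and .43 at 50.

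Assumptions: 1:1 allocation, no dropout, independent participants.

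**What to change.** In 5.2, replace the sentence on NUWAY's rates with text to this effect: retention and recurrence are compared between the randomised arms, with all randomised participants in the arm assigned, as a risk difference with 95% confidence interval and one named test, over one stated period after randomisation that is the same in both arms; NUWAY's general rates are shown as descriptive context only. The uncorrected chi-square would reproduce the two-sided powers in 17.2, but another single named test would serve.

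The sponsor should also:

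- choose the period and state how people still in treatment at its end are counted;
- for recurrence, state how people who left NUWAY are counted, since use after departure may not reach the treatment record;
- label these outcomes the same way in 3.1 and 5.2;
- make 17.2, 17.3 and 5.2 agree, in either direction: restate power for the number expected to be randomised, name the test, say that any retention power is conditional on the assumed rates, and say that abstinence is not powered.

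Cost: mostly wording, but the period and the counting rules are design decisions. Section 13.2 already plans to consult treatment records for all participants, including those who leave the study; the gap is substance use after leaving NUWAY. The between-arm estimate will be imprecise: about ±15 points for retention and ±21 for abstinence at 38 per arm, ±13 and ±18 at 50, possibly wider with group delivery. It may also look less favourable than the NUWAY comparison.
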